2.4 Endpoints

- Safety Endpoints: Skin reactions using the modified Berger Bowman irritation assessment scale and the incidence of AEs reported during the study.
- Efficacy Endpoints: Log_{10} CFU/cm² of resident microbes on skin before and after each product application at 30 seconds, 10 minutes and 6 hours on the abdomen and groin.
- Exploratory Endpoints: Product weight prior to product application (g) and post-product application (g) on the abdomen and groin.

2.5 Acceptance Criteria

To be included in the primary analysis [modified intent-to-treat (mITT) data set], a product application site must have a Product Application Day microbial baseline within the stated requirements. Table 1 summarizes the baseline criteria for the mITT data set for each anatomical site and the expected minimum efficacy country specific standards.

For HC primary objectives, it will declare success when and only when all four primary objectives pass HC analysis acceptance criteria.

For FDA primary objectives [10-minute (abdomen and groin) post-product application time point], it will declare success when and only when all four primary objectives pass FDA analysis acceptance criteria. For FDA secondary objectives [30-second (abdomen only) post-product application time point], a gatekeeping procedure will be applied: the efficacy analysis for two secondary objectives will be performed only when all four primary objectives [10-minute (abdomen and groin) post-product application time point] pass the acceptance criteria and it will declare success when and only when all four primary and two secondary objectives pass FDA analysis acceptance criteria.

For responder rate at 6 hours, no acceptance criteria are applied.

Table 1: mITT Data Set for Each Anatomical Site and Expected Minimum Efficacy Standards

Anatomical Product Application Site	Product Application Day Baseline Criteria	HC Analysis Acceptance Criteria at 30 Seconds, Primary Objectives	HC Analysis Acceptance Criteria at 6 Hours, Primary Objectives	FDA Analysis Acceptance Criteria at 30 Seconds, Secondary Objectives	FDA Analysis Acceptance Criteria at 10 Minutes, Primary Objectives
Abdomen	3.20 to 6.00 \log_{10} CFU/cm ²	Immediate effectiveness for the IP is at least a 2- \log_{10} CFU/cm ² reduction from baseline skin flora counts at 30 seconds.	Persistence effectiveness for the IP is at least a 2- \log_{10} CFU/cm ² reduction from baseline skin flora counts at 6 hours.	At 30 seconds the upper two-sided 95% confidence bound of the average treatment effect (ATE) of IP - AC should be less than 0.5 \log_{10} . At 30 seconds the lower two-sided 95% confidence bound of the ATE of NC - IP should be greater than 1.2 \log_{10} .	At 10 minutes the upper two-sided 95% confidence bound of the average treatment effect (ATE) of IP - AC should be less than 0.5 \log_{10} . At 10 minutes the lower two-sided 95% confidence bound of the ATE of NC - IP should be greater than 1.2 \log_{10} .
Groin	5.50 to 7.50 \log_{10} CFU/cm ²	Immediate effectiveness for the IP is at least a 3- \log_{10} CFU/cm ² reduction from baseline skin flora counts at 30 seconds.	Persistence effectiveness for the IP is at least a 3- \log_{10} CFU/cm ² reduction from baseline skin flora counts at 6 hours.	None	At 10 minutes the upper two-sided 95% confidence bound of the average treatment effect (ATE) of IP - AC should be less than 0.5 \log_{10} . At 10 minutes the lower two-sided 95% confidence bound of the ATE of NC - IP should be greater than 1.2 \log_{10} .

3 Sample Size

3.1 HC Analysis

To evaluate the primary efficacy objective for HC analysis a sample size of at least 192 evaluable sites per study product arm (IP or RS) per body site can achieve > 95% power to pass HC analysis acceptance criteria for all four objectives (IP only) using one-sample t-test (two-sided), with the following assumptions in Table 2.

Table 2: Parameters Used in Sample Size Calculations For HC Analysis

Two-sided test Type I error (α) : 0.05					
Time Point	Study Product	Standard Deviation for Log Reduction: Abdomen	Standard Deviation for Log Reduction: Groin	Log Reduction: Abdomen (\log_{10})	Log Reduction: Groin (\log_{10})
30 seconds	IP	1.14	1.43	3.47	3.38
6 hours	IP	1.22	1.24	3.43	3.50

3.2 FDA Analysis

To evaluate the primary and secondary objectives for the US FDA analysis a sample size of 280 evaluable sites per study product arm (IP, AC or NC) per body site can achieve > 95% power to demonstrate the non-inferiority of the Investigational Product (IP) as compared to the Active Control (AC) and the superiority of the IP as compared to the negative control (NC) in antimicrobial effect at 30-second (abdomen only) and 10-minute (abdomen and groin) post-product application time point for all six objectives, with the following assumptions in Table 3.

Table 3: Parameters Used in Sample Size Calculations For FDA Analysis

Two-sided test Type I error (α) : 0.05		
Average Treatment Effect	Abdomen (\log_{10})	Groin (\log_{10})
IP - AC	0.06	0.10
NC - IP	1.58	2.31
Standard deviation for each product on Abdomen: 1.05 \log_{10}		
Standard deviation for each product on Groin: 1.2 \log_{10}		

The overall power to pass both HC analysis and FDA analysis acceptance criteria is > 90%.

4 Intended Statistical Software

The analyses will be performed using R version 3.6.0 (2019-04-26) [2] or higher. R libraries and versions that are used for analyses will be listed.

5 Data

5.1 Database Information

Data will be captured by electronic case report forms (eCRFs) and provided to study statistician and statistical programmer by Data Management. More information on database management may be found in Data Management Plan for this study.

5.2 Data Sets Analyzed

- The full intent-to-treat (ITT) data set (all randomized subjects that received study product) will be used for the safety analysis.
- A modified intent-to-treat (mITT) data set will be used for efficacy analyses. Inclusion for the mITT data set is evaluated for each anatomical site (left and right for the groin and abdomen). For each anatomical site, product application day baseline criteria must be met (refer to Table 1 for product application day baseline criteria) in order to be included in the mITT data set.
- Analyses conducted on the mITT data set will also be conducted on the Per Protocol data set as supportive analyses when Per Protocol data are different from mITT data. The Per-Protocol data set will include evaluable product application sites from the mITT data set that adhere to defined assessments and procedures in the protocol central to patient enrollment, safety, rights or wellbeing, as well as the completeness, accuracy and reliability of study data.

5.3 Protocol Deviations and Use of Associated Data

Table 4 lists pre-defined potential protocol deviations and rules for use of associated data in analysis, which has been documented in a note-to-file “MPS-17IPVSS02_Guideline_Protocol_Deviations_Data_Use.pdf”. For any additional protocol deviations or issues that are not listed in Table 4, exclusion of the data from each population set will be reviewed and finalized on a case by case prior to the database lock.

All protocol deviations for this study will be listed (cf. Listing B.1). Any data that are excluded from any analysis will be listed indicating from which population sets data are excluded (cf. Listings B.2 for HC analysis and B.3 for FDA analysis).

5.4 Analysis Population Set(s)

For subject disposition, refer to Table A.1.1. Subjects who did not complete the study will be listed along with the status at the end of study (cf. Listing B.4).

For each analysis (HC analysis and FDA analysis), the number of subjects evaluable for ITT (randomized and treated/study product received), mITT and per-protocol (PP) analyses for CFU count and product weight per body site/location will be tabulated (cf. Tables A.1.2 for HC analysis and A.1.3 for FDA analysis). Subjects who were randomized and treated but did not pass the product application day baseline criteria (not eligible for mITT or PP analysis) will be listed (cf. Listing B.5).

Table 4: Guideline on Use of Associated Data in Analysis for Potential Protocol Deviations

Category	Description of Deviation (Examples)	Use of Associated Data in Analysis			
		mITT CFU count	PP CFU count	mITT weight	PP weight
Randomization error	Incorrect product applied based on randomization schedule or Subject received application of one or more incorrect products (grouped based on product applied)	Yes	No	Yes	No
	Subject received correct product but product was applied to incorrect side of the body based on randomization schedule				
	Sample taken from incorrect sample site within the treatment area based on randomization schedule				
Deviation from defined procedure	Loss of partial sampling volume	Yes	No	Yes	No
	Samples not plated in the 30 minute timeframe from collection				
	Subject leaves the study site but returns for assessments				
	Product application time outside of 30 seconds \pm 5 seconds on the abdomen or 2 minutes \pm 5 seconds on the groin				
Clinical assessment not done	Plates not dosed or plates contamination	No	No	No	No
Clinical assessment outside of window	Sampling time outside specified windows	Yes	No	Yes	No
Other	Pooling of samples from different subjects or different time points from the same subject	No	No	No	No
	Product weight error (difference in weights between pre application and post application less than 0 or greater than 2 grams)	Yes	Yes	No	No

6 Statistical Analysis/Calculations

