6.1 Derived Variables

6.1.1 Log₁₀ CFU/cm² of skin

Raw colony counts from each dilution will be recorded on the appropriate eCRFs for each subject. The average number of microorganisms recovered will be calculated using the formula below to convert the bacterial counts into log₁₀ CFU/cm² of skin:

$$R = \log_{10} \left[\frac{F \left(\frac{\sum_{i=1}^3 C_i}{n} \right) D}{A} \right] \quad (1)$$

Where:

R = the average CFU count in log₁₀ scale per cm² of skin.

F = Total number of mL of stripping fluid added to the sampling cylinder (6 mL). Note: If sample solution is lost during the procedure for a certain time point, the F value for that time point will change from 6 mL to the “Volume Remaining (mL)” recorded in the Core Lab Procedure Overview eCRFs.

$\frac{\sum_{i=1}^3 C_i}{n}$ = average of the triplicate colony counts used for each sample collected (n = 3).

D = Dilution factor of the plates counted. One of 10⁰, 10¹, 10², 10³, 10⁴, or 10⁵.

A = Inside area of the sampling cylinder in cm² (3.80 cm²).

The average CFU/mL, CFU/cm², and log₁₀ CFU/cm² will be calculated for samples from each product application site in the same manner.

In order to avoid potential calculation problems due to taking the logarithm of zero, values of less than 1 CFU/cm² will be treated as 1 CFU/cm², such that the log₁₀ transformation is not less than zero.

If colonies on one of the plates are uncountable, the average count from the remaining plates will be used. If colonies on two of the plates are uncountable, the count from the remaining plate will be used. If colonies on three plates are all uncountable, the average count will be missing.

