6.1.4 Product Weight

The weight (grams) of product solutions applied to an anatomical area will be estimated as:

Product weight prior to product application (g) - product weight post-product application (g)

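### SAP Table 4 discards valid product weights for plate faults and pooled samples, and does not say how many bad plates exclude a CFU count

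*SAP*

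**What the plan says.** SAP section 5.4, Table 4, sets out which data are used after each kind of protocol deviation. It has separate columns for CFU count and product weight, each for the mITT and PP sets.

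- The row "Plates not dosed or plates contamination", in the category for assessments not carried out, reads No in all four columns.
- The row "Pooling of samples from different subjects or different time points from the same subject" also reads No in all four columns.
- The weight-error row, for a difference below 0 g or above 2 g, reads Yes for both CFU columns and No for both weight columns.

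Protocol 6.1.6.3 and SAP 6.1.4 define product weight as the pre-application weighing minus the post-application weighing. SAP 2.4 lists it as an exploratory endpoint. Protocol 13.5.5 and SAP 6.2.2.1 give it descriptive statistics only.

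Protocol 6.3.3 has each dilution plated in triplicate. On lost plates, SAP 6.1.1 says: "If colonies on one of the plates are uncountable, the average count from the remaining plates will be used". It goes on to use a single remaining plate when two are uncountable, and sets the value to missing only when all three are.

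**The concern.** A plating fault or a pooled sample says nothing about how much solution left the applicator. Table 4 recognises that the two measures are separable when the weight is at fault, because it then keeps the CFU count. It does not apply the same logic when the plate is at fault.

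The second matter touches the primary data. The plate row gives no number of plates, does not define contamination, and does not refer to 6.1.1; nor does 6.1.1 refer to Table 4. If one plate of three is contaminated, the analyst could drop the count under Table 4 or average the other two under 6.1.1. Protocol 3.3.2.2 names the SAP's deviation rules as a measure to control bias, so each event should have one answer fixed in advance.

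**Working it through.** The plan states no figure on this point, so there is none to reproduce. The documents also give no fault rate. All rates below are assumptions, and faults are taken as independent.

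**Weights lost**

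1. Samples that matter: three per site (30 seconds, 10 minutes, 6 hours; Protocol 6.3.1). The baseline sample is left out. If it is lost, the site has no qualifying baseline and leaves the mITT set under SAP 5.2 whatever Table 4 says about weight.
2. Assumed fault rate per sample: p = 0.5% to 2%. One faulty sample is taken to remove the site's single weight.
3. Share of sites losing a weight: 1 − (1 − p)³.
   - p = 0.005: 1 − 0.995³ = 1.49%; 280 × 0.0149 = 4.2 sites.
   - p = 0.02: 1 − 0.98³ = 5.88%; 280 × 0.0588 = 16.5 sites.
4. Standard error of the mean weight, relative to no loss: 1/√(1 − loss).
   - 1/√0.9851 = 1.008.
   - 1/√0.9412 = 1.031.

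**Plates: the two readings side by side**

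Let q be an assumed contamination rate per plate, with three plates at the counted dilution. If any bad plate excludes the sample, the loss is 1 − (1 − q)³. If only three bad plates do so, as 6.1.1 would have it were contaminated plates treated as uncountable, the loss is q³.

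| q | Any bad plate excludes | Sites of 280 | Only all three exclude | Sites of 280 |
|---|---|---|---|---|
| 0.1% | 0.30% | 0.8 | 1 × 10⁻⁹ | below 0.001 |
| 1% | 2.97% | 8.3 | 1 × 10⁻⁶ | below 0.001 |
| 5% | 14.3% | 39.9 | 1.25 × 10⁻⁴ | 0.035 |

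These are losses per sample. Under the any-plate reading, a baseline sample excluded for one bad plate would cost all three post-application time points at that site.

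**Context: power for the FDA objectives**

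The plan states more than 95% for all six objectives at 280 sites per arm. With Φ(δ/(σ√(2/n)) − 1.96) and δ the distance from the margin:

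- abdomen non-inferiority, δ = 0.5 − 0.06 = 0.44, σ = 1.05: 0.9986 (used twice)
- groin non-inferiority, δ = 0.5 − 0.10 = 0.40, σ = 1.2: 0.9764
- abdomen superiority, δ = 1.58 − 1.2 = 0.38, σ = 1.05: 0.9899 (used twice)
- groin superiority, δ = 2.31 − 1.2 = 1.11, σ = 1.2: 1.0000

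The product is 0.954, which agrees with the plan. Under the any-plate reading, with lost samples not replaced, q = 1% gives n = 280 × 0.99³ = 271.7 and power 0.9465.

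**The case against.** **The two plate rules may not conflict.** A reader might infer that Table 4 contradicts 6.1.1. The documents do not establish that. 6.1.1 speaks of uncountable plates. The Table 4 row speaks of plates in the plural, under a category for assessments not done, and can be read as a sample that yielded no usable plate. On that reading it matches the 6.1.1 rule that the value is then missing. The rules diverge only if contaminated or undosed plates count as uncountable and only one or two are affected. This objection stands. What remains is an overlap with no stated precedence.

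**A bad plate need not be a counted plate.** Treatment-day samples are plated at three to six dilutions, and the formula uses only the plates counted. Contamination at an unused dilution need not matter. This also stands, but Table 4 does not say so.

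**PP weight in other rows.** A reader might extend the point to "Samples not plated in the 30 minute timeframe from collection", "Loss of partial sampling volume" and "Sampling time outside specified windows", where PP weight is also No. SAP 5.2 defines PP by sites whose handling followed protocol procedures, so excluding such a site's data from a supportive set is within the definition, and mITT weight stays Yes for all three. The same argument could be pressed for the PP weight cells in the plate and pooling rows. It cannot justify the mITT cells.

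**Associated data may be meant per time point.** A weight has no time point, and the weight columns still read No, so this reading does not rescue the table.

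**The stakes are low.** The weight endpoint is exploratory and descriptive, and exclusions are listed individually in Listings B.2 and B.3. This is correct and bounds the importance of the point.

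**Conclusion.** The weight part holds on the text: Table 4 removes valid weights from the mITT and PP sets because of plate faults and pooling, neither of which bears on the weighing. At the assumed 0.5% to 2% per sample, 1.5% to 5.9% of sites (about 4 to 16 of 280) are affected and the standard error rises by about 1% to 3%. No bias is expected and no acceptance criterion uses the endpoint.

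The CFU part is an ambiguity in the handling of primary data. Its size depends on a plate contamination rate the documents do not give and on which reading the analyst adopts.

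It would be tempting to conclude that the FDA power is compromised, because 0.954 lies close to the stated bound. The documents do not support that: the rate is assumed, the any-plate reading is not established, and Protocol 3.3.1 allows further enrolment to reach the required number of evaluable sites. How far enrolment would make up for lost post-application counts is uncertain, since Protocol 4.0 ties it to the baseline criteria.

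This is a minor improvement worth making.

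**What to change.** Before database lock:

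1. In Table 4, set mITT and PP weight to Yes in the plate-fault and pooling rows, subject to the existing weight-error row. Leave the CFU entries for pooled samples at No.
2. In the plate-fault row, apply the CFU No only when no plate at the counted dilution is usable.
3. In 6.1.1, state that contaminated or undosed plates are treated as uncountable, so that the remaining plates are used. A reference from Table 4 alone would not settle the matter, because 6.1.1 does not currently mention contamination.
4. Make the same changes in the note-to-file that SAP 5.3 names as the source of Table 4.
5. Leave the PP weight entries for other procedural deviations as they are.

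The cost is a few edits to the SAP and the note-to-file. Data collection, study conduct and sample size do not change.

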6.1 Derived Variables

6.1.1 Log₁₀ CFU/cm² of skin

Raw colony counts from each dilution will be recorded on the appropriate eCRFs for each subject. The average number of microorganisms recovered will be calculated using the formula below to convert the bacterial counts into log₁₀ CFU/cm² of skin:

$$R = \log_{10} \left[\frac{F \left(\frac{\sum_{i=1}^3 C_i}{n} \right) D}{A} \right] \quad (1)$$

Where:

R = the average CFU count in log₁₀ scale per cm² of skin.

F = Total number of mL of stripping fluid added to the sampling cylinder (6 mL). Note: If sample solution is lost during the procedure for a certain time point, the F value for that time point will change from 6 mL to the “Volume Remaining (mL)” recorded in the Core Lab Procedure Overview eCRFs.

$\frac{\sum_{i=1}^3 C_i}{n}$ = average of the triplicate colony counts used for each sample collected (n = 3).

D = Dilution factor of the plates counted. One of 10⁰, 10¹, 10², 10³, 10⁴, or 10⁵.

A = Inside area of the sampling cylinder in cm² (3.80 cm²).

The average CFU/mL, CFU/cm², and log₁₀ CFU/cm² will be calculated for samples from each product application site in the same manner.

In order to avoid potential calculation problems due to taking the logarithm of zero, values of less than 1 CFU/cm² will be treated as 1 CFU/cm², such that the log₁₀ transformation is not less than zero.

If colonies on one of the plates are uncountable, the average count from the remaining plates will be used. If colonies on two of the plates are uncountable, the count from the remaining plate will be used. If colonies on three plates are all uncountable, the average count will be missing.

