6.3.2 Microbial Sample Collection / Scrub Cup Technique

Quantitative cultures (baselines and post product application) will be obtained by a modification of the cylinder sampling technique of Williamson-Kligman scrub cup technique. To collect the samples, a sterile scrub cup (2.20 cm I.D., skin surface area of 3.80 cm²) will be placed on the site and held firmly to the skin. Sampling solution (SS) (3.0 mL) will be pipetted into the cup and the skin will be scrubbed with moderate pressure for one minute using a sterile rubber policeman. Using a sterile transfer pipette, the SS will be removed and placed in a sterile test tube. An additional 3.0 mL of fresh sampling solution will be pipetted into the cup and the scrub procedure will be repeated. This solution will be pooled with the first solution collected.

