6.3.3 Bacterial Enumeration Methods

Following sample collection, 10-fold serial dilutions (1 mL sample + 9 mL PBW) will be prepared using PBW. One-mL aliquots of appropriate dilutions will be pour-plated in triplicate using trypticase soy agar containing neutralizers (TSA+N). Samples must be plated within 30 minutes of collection.

Serial dilutions of collected baseline screening samples as follows:

- for groin sites: 1 serial dilution (10^{-3})
- for abdomen sites: 1 serial dilution (10^{-1})

Serial dilutions of collected treatment day (D0) samples as follows:

for groin sites

- Baseline: 3 serial dilutions (10^{-3} , 10^{-4} and 10^{-5})
- 30 seconds: 6 serial dilutions (10^0 , 10^{-1} , 10^{-2} , 10^{-3} , 10^{-4} and 10^{-5})
- 10 minutes: 6 serial dilutions (10^0 , 10^{-1} , 10^{-2} , 10^{-3} , 10^{-4} and 10^{-5})
- 6 hours: 6 serial dilutions (10^0 , 10^{-1} , 10^{-2} , 10^{-3} , 10^{-4} and 10^{-5})

for abdomen sites

- Baseline: 3 serial dilutions (10^{-1} , 10^{-2} and 10^{-3})
- 30 seconds: 4 serial dilutions (10^0 , 10^{-1} , 10^{-2} and 10^{-3})
- 10 minutes: 4 serial dilutions (10^0 , 10^{-1} , 10^{-2} and 10^{-3})
- 6 hours: 4 serial dilutions (10^0 , 10^{-1} , 10^{-2} and 10^{-3})

After 72 ± 4 hours of aerobic incubation at $30 \pm 2^\circ\text{C}$, colonies will be counted and viable cells in the original sample will be calculated according to Standard Operating Procedures (SOPs). After incubation, plates may be refrigerated up to 48 hours prior to counting.

Raw colony counts from each dilution will be recorded on the appropriate CRFs for each subject. The average number of microorganisms recovered will be calculated using the formula to convert the bacterial counts into \log_{10} CFU/cm² of skin:

$$R = \log_{10} \left[\frac{F \left(\frac{\sum_{i=1}^3 c_i}{n} \right) D}{A} \right]$$

Where: R = the average CFU count in \log_{10} scale per cm² of skin.

F = total mL of sampling solution (SS) added to the sampling cylinder (6 mL);

$\frac{\sum_{i=1}^3 c_i}{n}$ = average of the triplicate colony counts used for each sample collected

D = Dilution factor of the plates counted. One of 10^0 , 10^1 , 10^2 , 10^3 , 10^4 , or 10^5 .

A = Inside area of the sampling cylinder (3.80cm²)

The average CFU/mL, CFU/cm², and \log_{10} CFU/cm² will be calculated for samples from each product application site in the same manner.

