RandID	Body Location	Product	Did Sampling Fluid from Sampling Site Extend to Other Remaining Sites at Any Time Point	Time Points Affected
Rxxxx			Yes	30 Seconds
Rxxxx			Yes	
Rxxxx			Yes	
Rxxxx			Yes	

Table B.9: Procedure Overview - Dressing Application

RandID	Body Location	Product	Was Dressing Application Placed on the Application Site at the 10 Minute Time Point	Was Dressing Integrity Compromised at Any Time Prior to the 6 Hour Time Point	Details
Rxxxx			Yes	Yes	Subject Confirmed Dressing was Adjusted and/or Touched
Rxxxx			Yes	Yes	
Rxxxx			Yes	Yes	
Rxxxx			Yes	Yes	

Table B.10: Core Lab Procedure Overview - Sample Solution

RandID	Body Location	Product	Was Any Sampling Solution Lost at Any Time During the Procedure	Time Point Affected	Volume Remaining (mL)
Rxxxx			Yes	Baseline	
Rxxxx			Yes		
Rxxxx			Yes		
Rxxxx			Yes		

Table B.11: Product Failures/Lab Accidents/User Errors

RandID	Are There Any Product Failures/Lab Accidents/User Errors to Report	Date of Incident	Product Affected	Time of Incident	Incident Code	Details	Was Product Used on Study Subject	Was an AE Associated with the Incident
Rxxxx	Yes			During Product Exposure	Product Handling Issue			
Rxxxx	Yes							
Rxxxx	Yes							
Rxxxx	Yes							

C Figures

C.1 HC Analysis

[figure not shown]

Figure C.1.1: mITT/PP - Log Reduction with 95% CI (Example Data Only)

C.2 FDA Analysis

[figure not shown]

Figure C.2.1: mITT/PP - ATE with 95% CI (Example Data Only)

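### After sample fluid is lost, SAP 6.1.1 replaces the 6 mL volume factor with the volume remaining (V), which under-counts a pooled sample by log10(6/V): 0.08 log at 5 mL left, 0.18 log at 4 mL left

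*SAP*

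**What the plan says.** SAP 6.1.1 defines F as "Total number of mL of stripping fluid added to the sampling cylinder (6 mL"), and protocol 6.3.3 defines it in the same way: "F = total mL of sampling solution (SS) added to the sampling cylinder (6 mL"). The SAP alone adds a note: when sample solution is lost at a time point, "the F value for that time point will change from 6 mL to the" volume remaining, as recorded in the Core Lab Procedure Overview eCRF.

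Protocol 6.3.2 describes two scrubs of 3.0 mL each. Of the second it says: "This solution will be pooled with the first solution collected." Protocol 6.3.3 then plates 1 mL aliquots of the appropriate dilutions in triplicate.

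Table 4 (SAP 5.4) lists "Loss of partial sampling volume" as a deviation whose counts stay in mITT and leave PP. mITT is the efficacy set, and for a site to enter it SAP 5.2 says that "product application day baseline criteria must be met". Listing B.10, called from SAP 6.5, has the column "Was Any Sampling Solution Lost at Any Time During the Procedure", with the time point affected and the volume remaining.

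**The concern.** F converts CFU per mL into total CFU washed off the skin. That total depends on the volume the organisms were suspended in, which is the volume added. If mixed fluid is then spilled, the remainder has the same concentration. Multiplying by V counts only the organisms still in the tube and drops those in the lost fluid. The note therefore departs from the SAP's own definition of F and from the protocol formula.

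The result feeds every efficacy endpoint:

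- A mixed loss on a post-application sample lowers the count and overstates that site's log reduction at that time.
- A mixed loss at baseline understates the reduction at 30 seconds, 10 minutes and 6 hours together. It can also move the site across an mITT baseline limit.
- The HC criteria are single-arm, so there is no comparator in which the error could cancel. In the FDA contrasts the direction depends on which arm is affected, and equal loss in all arms roughly cancels.

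**Working it through.** **Inputs.** Volume added: 3.0 + 3.0 = 6.0 mL (protocol 6.3.2), which reproduces the stated F. Area: π × (2.20/2)² = 3.80 cm², as stated. Formula: R = log10(F × mean plate count × D / A). Floor: values below 1 CFU/cm² are set to 1. V = 5 and V = 4 mL are illustrations, because the documents give no expected volume or frequency of loss.

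**Mixed fluid.** The mean count × D is CFU per mL and does not change with the loss. Error of F = V is log10(V/6):

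- V = 5: log10(5/6) = −0.079
- V = 4: log10(4/6) = −0.176

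A Poisson simulation of triplicate plates with a true value of 3.198 returned 3.198 with F = 6, and 3.118 (5 mL left) and 3.022 (4 mL left) with F = V.

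**How large a loss is plausible.** Post-application samples are plated undiluted in triplicate (3 mL), and 1 mL more starts the dilution series. So 4 mL left is about the largest loss that still allows full post-application plating. Baseline plating starts from a diluted sample, so a larger loss could stay analysable there (3 mL left: log10(6/3) = 0.301).

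**Unmixed fluid.** Let r be the concentration of the lost fluid divided by that of the fluid kept. The true total is proportional to V + r(6 − V). The error with F = 6 is log10[6/(V + r(6 − V))]. With F = V it is log10[V/(V + r(6 − V))], which is never above zero. At V = 4:

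| r | error, F = 6 | error, F = V |
|---|---|---|
| 0 | +0.176 | 0.000 |
| 0.25 | +0.125 | −0.051 |
| 0.5 | +0.079 | −0.097 |
| 1 | 0.000 | −0.176 |
| 2 | −0.125 | −0.301 |

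The two errors are equal in size at r = (√(6V) − V)/(6 − V). This is 0.477 at V = 5 and 0.449 at V = 4. Above that ratio F = 6 is nearer the truth; below it F = V is nearer.

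**Floor.** With 0 or 1 colony in total on three undiluted plates, F = 6 and F = 4 both give 0. With 2 colonies they give 0.022 and 0. From 3 colonies (0.198 and 0.022) the full 0.176 applies.

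**Baseline eligibility, mixed loss, 4 mL left.** The affected bands run from each limit to the limit + 0.176:

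- Wrongly excluded: true abdomen 3.20–3.37 and groin 5.50–5.67. For example, abdomen 3.30 reads 3.12.
- Wrongly admitted: true groin 7.51–7.67.
- Abdomen 6.01–6.17 would be wrongly admitted only if the plates can be counted. The highest abdomen baseline dilution is 10⁻³, so the plates carry 10^6.01 × 3.80/6/1000 ≈ 648 to 10^6.17 × 3.80/6/1000 ≈ 937 colonies. The documents state no countable limit, and SAP 6.1.1 makes a sample missing when all three plates are uncountable.

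**Arm means.** Shift in mean log reduction = (share of post-application samples affected − share of baseline samples affected) × log10(6/V). Assume 5–10% of IP post-application samples and no baseline samples:

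- V = 4: 0.05 × 0.176 = 0.009 to 0.10 × 0.176 = 0.018
- V = 5: 0.05 × 0.079 = 0.004 to 0.10 × 0.079 = 0.008
- Equal shares: about 0

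For groin at 30 seconds (planning SD 1.43, n = 280), SE = 1.43/√280 = 0.085, so 0.009–0.018 is 0.1–0.2 SE. At the planned reduction of 3.38 the expected lower 95% bound is 3.21, which is 0.21 above the criterion of 3.

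**The case against.** **Neither value of F is right in general.** The two scrubs are separate until pooled, and the SAP itself lists sampling fluid that spreads to other sites (Listing B.8). Fluid that leaks early in a scrub, or during the second scrub, may carry few organisms. F = V is then nearer, and F = 6 over-counts by up to 0.176 at 4 mL left. This stands, and it is why F = V should remain as a sensitivity run. It does not justify F = V as the default, because that rule never errs high and is exact only for organism-free losses.

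**Existing safeguards.** The rule is pre-specified and applies to all products, and enumeration is blinded. PP drops the affected samples, and Listing B.10 discloses them. This limits the severity, but the primary set still uses the under-counted values.

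**Unseen sources.** The eCRF and the site's counting SOPs are not among the documents. A reader might infer from Listing B.10 that the stage of loss is never recorded. That listing is only an output shell, so the inference is not supported. For the same reason, the lack of a lost-fluid rule in the protocol does not show that the site has none.

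**Size.** The arm-mean scenario gives every affected sample about the largest workable loss and ignores the floor, where some IP abdomen counts are likely to sit. It is near worst case, so its results are upper figures.

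**Conclusion.** The substitution is wrong as written for mixed fluid. The error per affected sample is log10(6/V), or 0.08 log at 5 mL left and 0.18 log at 4 mL left, and less near the floor. It enters the primary analysis set and can change baseline eligibility for individual sites.

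A reader might infer that the rule tilts the trial towards success. The documents do not support that. They give no loss frequency and no reason to expect loss to differ by arm, and baseline losses push the other way. Under the assumed one-sided 5–10% loss the mean shifts by at most 0.009–0.018 log, and at the planning values no conclusion is expected to change.

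A reader might also infer that abdomen baselines just above 6.00 would certainly be admitted. That depends on plates of about 650–940 colonies being countable, which the documents do not settle.

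Severity: minor. The 0.08 and 0.18 figures assume the lost fluid was as concentrated as the fluid kept.

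**What to change.** In SAP 6.1.1, keep F = 6 mL (volume added, as in the protocol formula) as the mITT default for samples with lost fluid. Use a smaller F only if less than 6 mL was added. Repeat the mITT analysis, including baseline eligibility, with F = V as a sensitivity analysis based on the recorded volume remaining and time point. Keep the PP exclusion.

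The two runs bracket the true count when the lost fluid was no more concentrated than the fluid kept (r ≤ 1). The downside is that F = 6 over-counts when the lost fluid carried few organisms, and the sensitivity run covers that case.

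The cost is one sentence in the SAP and one extra run. The volume and time point are already captured, so no new data are needed.
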